9.0. Design Considerations to Enhance Rigor, Reproducibility and Impact: A number of our methodological design decisions were determined by our pilot R21 findings. A limitation of many studies on STI risk reduction interventions for women is the imbalance in intensity of sessions between the experimental intervention and control group, which makes it difficult to determine if intervention differences are attributable to differences in attention between the conditions or to the "active ingredients" of the intervention. Our control condition will be matched for time, attention, and information, and will provide a rigorous test of the effect of HCEM. Follow-up assessments will be administered by RAs who are blinded to treatment assignment (and not by the same RAs who administers the intervention). Our study sites reflect considerable socioeconomic and ethnic/racial diversity, and higher rates of STIs and substance use, which will allow for generalizability of the results beyond one study site.

10.0. Limitations and Countermeasures: Limitations of the current study include: potential issues related to disclosure of sensitive information, the use of self-report, assessment reactivity and effect on measured outcomes, the inclusion of only English-speaking participants, and generalizability of study results to other populations. To address these study limitations: 1) We will use technology to minimize socially desirable responses, particularly with stigmatizing behaviors, 2) we will directly assess and adjust for social desirability bias, 3) the baseline computerized assessment will occur prior to randomization to minimize bias; 4) loss to follow-up will be limited by computer-based assessment and home visits during postpartum assessment, and by our experience with long-term follow-up of high risk, vulnerable samples of women; 5) the information-matched control condition has been found acceptable and engaging in at least 4 behavioral studies that we know of including our own previous trials, and 6) based on data available at the clinic sites, there is only a small percent of women who are Spanish-speaking only. While participants will be recruited as close to first prenatal visit as possible, we will also include eligible high-risk women who are at later stages of pregnancy; we will adjust analyses for baseline pregnancy stage and assessment timing, as well as delivery status (delivered/not delivered) at follow up assessments in our data analysis, and pregnancy loss during course of study (e.g., miscarriage or stillbirth). We include monogamous pregnant women because STI risk is significantly elevated when substance abuse is present, regardless of partner status. Moreover, in our R21 study, 86% of the sample was monogamous, and yet intervention reduced condomless sex and substance abuse. We decided not to include genital herpes as an STI outcome as this is not in the clinical guidelines for STI screening set forth by the CDC. [name] will determine on a case-by-case basis for consideration of serological testing of genital herpes based on clinical presentation (e.g., active lesion) or partner history.

11.0. Project Timeline: We include a timeline detailing the proposed study activities (see Table 2, below).

11.1. Table 2. Planned Study Timeline		Year 1				Year 2				Year 3				Year 4				Year 5			
		1	2	3	4	1	2	3	4	1	2	3	4	1	2	3	4	1	2	3	4
HCEM Refinement, IRB, Hiring/Training Staff																					
Recruitment																					
Baseline / Follow-ups, Barriers Assessment																					
Data Analysis/Publications																					

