5.1. Inclusion/exclusion criteria: Participants will be 250 pregnant women (as close as possible to first prenatal visit), age 18 or older, and will follow similar recruitment to the R21 study given feasibility and acceptability rates. Specifically, the study will include pregnant women who endorse: 1) at least one unprotected vaginal (or anal) sex occasion (USO) in the past 30 days (supported by the literature for our “high risk” sample, identified as such based on childbearing age, urban, ethnically diverse, and reporting co-morbid recent history of substance use), and 2) having more than one male partner in the last 6 months and/or having uncertainty about current sexual partner’s monogamy, and 3) current alcohol/drug use risk, 4) currently resides in the state of Michigan. Exclusion criteria include: 1) inability to provide informed consent (e.g., clear cognitive impairment), or 2) inability to understand English.

5.2. Recruitment: We successfully completed the R21 study in a prenatal clinic in Providence, Rhode Island. We will implement similar methods to recruit for the proposed study. Past year public health data reports increases in STI cases reported in Washtenaw County (Michigan). Recruitment will take place in a number of ways, including in-person at clinical sites within Michigan Medicine, other Michigan based clinics, or remotely. Remote recruitment for Michigan Medicine patients will happen by a member of the research team conducting a chart review (MiChart) and contacting prenatal patients over the phone, via physical mail, or through email messages. The research team will also recruit online by advertising on the University of Michigan Health Research website (<https://umhealthresearch.org>) or through social media platforms (e.g. Facebook, Instagram). Online/remote recruitment will not be limited to Michigan Medicine patients, however; pregnant women residing in the state of Michigan who are patients of outside

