Screener items (embedded with general health questions):

1. Questions for history of STI sexual risk (i.e., number of occasions of condomless vaginal (and anal) sex in the past 30 days);
2. T-ACE (four questions) is a screen for risk drinking developed for use in OB/GYN settings;
3. Substance Use Risk-Profile Pregnancy Scale (SURP-P) (three questions) this screening is specifically designed to quickly identify obstetrical patients at risk for alcohol or illicit drug use.

Table 1. Study Measures		Antenatal		Postpartum
Self-report measures	Baseline	19-28 weeks	36-39 weeks	6 weeks
Demographic Information	X			
Marlowe-Crowne Social Desirability – Short Form	X			

Timeline Follow-back, sex, alcohol, drug use	X	X	X	X
Condom Use Self-Efficacy	X	X	X	X
Treatment Self-Regulation Questionnaire	X	X	X	X
HIV/STI Knowledge Questionnaire	X	X	X	X
Risk Perceptions Items (STI)	X	X	X	X
Importance, Readiness, and Confidence Rulers	X	X	X	X
Condom Attitude Scale	X	X	X	X
Perceived Competence Scale	X	X	X	X
COVID-19 Family Stress Screener	X	X	X	X
Objective biometric measures				
Urine or Vaginal Swab Collection: STI Testing	X*	X	X	X
Birth Outcomes				X
Hair Sample Testing (suspended 11/2022)	X**		X**	
Economic and implementation measures				
Costs Analysis	X	X	X	X
Clinic staff surveys	X			

*In-person, Michigan Medicine visits only.

**A urine sample may be collected in place of a hair sample in the event that a hair sample cannot be collected.

The following assessment measures will be administered at the baseline assessment:

1. Demographic information, including age, race, ethnicity, marital/partner status, parity, employment, socioeconomic status.
2. *Marlowe-Crowne Social Desirability Scale-Short*,¹¹⁴ includes 13 items sensitive to social desirability bias.

5.5.2 Primary Outcome Measure:

1. *Unprotected sexual occasions (USOs)* at the 8-week follow-up assessment.

USOs will be obtained from the *Timeline Follow-Back (TLFB)* to assess sex-risk behaviors at baseline and follow up assessments. The TLFB is a calendar assisted structured interview that provides a way to cue memory so that accurate recall is enhanced for event-level data; it has been used to assess sexual risk-taking. USOs will be assessed in the 90 days prior to the baseline, as well as the 8-week follow-up assessments.

5.5.3 Secondary Outcome Measures:

1. *Alcohol use and Illicit drug use*: Self-reported days of alcohol and illicit drug use at 8-week assessment.

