The TLFB will be used to measure alcohol use by using the variable of percent days abstinent. Illicit drug use will also be collected from the TLFB, and measured by using the “yes/no” variable for each day. Both variables will be assessed in the 90 days prior to the baseline, as well as the 8-week follow-up assessments.

Other Outcomes:

A. *Alcohol use*: In addition to the percent days abstinent variable, the TLFB will be used to measure drinks per drinking day and heavy episodic drinking episodes.

B. *Illicit drug use*: While not a primary outcome measure, the study has collected objective hair measures at various points through the duration of the research study (1.5-inch samples) providing up to a 90-day window (by Psychemedics, Inc.) to corroborate self-reported drug use at follow-up assessments (see *Data Analysis* section, below), as well as urinalysis. Our team has experience from our pilot study with feasibility of obtaining hair samples from pregnant women; we

improved upon our ability to collect hair samples as the study progressed (e.g., reducing refusal rates by 45% and obtaining samples from 85% of participants). In the case that a hair sample was not obtained, the team attempted to collect a urine sample instead. The urine samples were collected by a trained RA, which corroborated the self-report of drug use in the prior 30 days. Results were read by the RA after 5 minutes, and then the sample discarded. Results, reported by study ID, will be transferred by secure, encrypted electronic file and downloaded to a secure Michigan Medicine server. The study team has discontinued this measure (participants enrolled in November 2022 and on), as collecting hair samples has become increasingly difficult due to the COVID-19 pandemic and the expanding locations of our participant population. These challenges have made meeting participants in-person for sample collection challenging.

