7.0. Data Analysis: Descriptive statistics will be calculated to summarize baseline characteristics for the full cohort and by intervention arm. Quality inspection will be carried out periodically to screen for missing-ness and data anomalies, and entry error. T-tests and chi-square-tests will be used to compare study arms with respect to demographic characteristics and baseline measures of unprotected sex and alcohol/drug use. Any identified confounders with $p \leq 0.10$ will be included in all subsequent analyses. Using the TLFB, we estimate the frequency of number of days in the 90-day period that the participant is engaged in a risky behavior. This will be carried out separately for each of the outcomes, namely, unprotected sex, illicit drug use and alcohol use, and heavy episodic drinking days (Hypothesis 1 and 2). The outcomes will be analyzed under a clustered count regression framework (Poisson or Negative Binomial) with frequency as outcome, and time (baseline, 2 months, 6 months), group (HCEM, control) and time-by-group interaction as the primary covariates. A generalized linear mixed models (GLIMMIX) approach will be adopted assigning a random subject intercept to account for the clustering within each participant. The regression model will be further controlled for potential confounders such as demographic characteristics, social desirability, and other variables that are identified to be significantly associated with outcome in the univariate analyses. We will adjust analyses for baseline pregnancy stage and assessment timing, as well as delivery status (delivered/not delivered) at follow up assessments in our data analysis, and pregnancy loss during course of study (e.g., miscarriage or stillbirth). Changes over time within each group will be estimated post-hoc by sliced effects derived from the regression model. In additional analysis, reduction in proportion of participants engaged in the risky behavior on ≥ 1 days within the 90-day period will be analyzed using a clustered logistic regression with a dichotomous outcome at the subject level indicating the status of the engagement, and with time (baseline, 2 months, 6 months), group (HCEM, control), time-by-group interaction as the primary factors. As before, a random subject intercept will account for the clustering and the model will be controlled for the same ensemble of covariates as in the case of the count regression models. Similar analyses will be conducted in the secondary aims for the outcomes that will be measured postpartum. To test hypothesis 3a and 3b, we will use structural equation modeling (SEM) approach. These include pregnancy-specific measures of autonomous motivation, self-efficacy, knowledge and risk perceptions (see Table 1). These measures are all continuous and will be measured at all three time points. All relevant direct and indirect effects will be evaluated. Significance of the indirect effect of the mediators will be tested using bootstrap method which appears to have good power in small samples. Birth outcome data will be available to the team by accessing patient medical records postpartum (Hypothesis 2c).

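### The look-back for the week-8 primary outcome is not clearly defined; on the likelier 90-day reading, a day-56 visit counts 34 pre-randomisation days (38%), which dilutes the effect without biasing the test

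*Combined protocol and SAP*

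**What the plan says.** Section 5.5.2 names USOs at the 8-week follow-up as the primary outcome, taken from the Timeline Follow-Back (TLFB): "USOs will be assessed in the 90 days prior to the baseline, as well as the 8-week follow-up assessments". Section 5.5.3 uses the same construction for the week-8 alcohol and drug outcomes: "Both variables will be assessed in the 90 days prior to the baseline, as well as the 8-week follow-up assessments".

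Section 7.0 describes the analysis variable without distinguishing visits: "Using the TLFB, we estimate the frequency of number of days in the 90-day period that the participant is engaged in a risky behavior". That frequency enters one count model with baseline, 2 months and 6 months as time levels, group, and their interaction, with a random subject intercept. An additional binary analysis again uses engagement on at least one of the "days within the 90-day period will be analyzed using a clustered logistic regression with a dichotomous outcome".

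Section 4.0 places the follow-ups at 8 and 24 weeks, while Table 1 lists the first antenatal follow-up as 19-28 weeks. Section 10.0 says "the baseline computerized assessment will occur prior to randomization to minimize bias". The only provision about timing, in 7.0 and 10.0, is covariate adjustment: "We will adjust analyses for baseline pregnancy stage and assessment timing". No section cuts the week-8 window at randomisation, uses days assessed as an exposure, or plans an analysis of post-randomisation days only.

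**The concern.** Eight weeks is shorter than 90 days. If the look-back is 90 days at both visits, part of the week-8 outcome was lived before the woman was randomised, and treatment cannot change it. The same days are counted at baseline as well, so baseline and week 8 share data beyond what a random subject intercept describes. An assessment-timing covariate neither removes those days nor sets the exposure.

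At stake are the size of the estimated effect on the primary outcome and the trial's sensitivity to it. The binary analysis has an additional difficulty. Entry requires "at least one unprotected vaginal (or anal) sex occasion (USO) in the past 30 days" (5.1). If screening and baseline fall on the same day, that whole 30-day period lies inside the 34 overlapping days, so a woman can count as engaged at week 8 solely because of the event that qualified her. That sits badly with the 50% drop anticipated in 7.4.

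**Working it through.** **Inputs.** Look-back 90 days (5.5.2 read with 7.0). Visit at 8 weeks = day 56 (4.0). Baseline mean 36 days, follow-up means 32 (control) and 29 (HCEM), 100 evaluable women per arm, 5% level, clinically significant difference 10 days (7.4). Assumptions added here: day 0 is the baseline session, a constant rate within each period, a treatment effect from day 0, a two-sided test and, unless stated otherwise, Poisson variance.

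**Overlap = 90 - visit day.**
- Day 56: 34 days, 34/90 = 38%.
- Day 61 (two calendar months): 29 days, 32%.
- Day 63: 27 days. Day 84: 6 days. Day 90 or later: none.
- 24 weeks (day 168): the window starts at day 168 - 90 = 78, so no overlap.

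**Dilution at day 56.** An absolute effect is multiplied by 56/90 = 0.62.
- 10 days becomes 10 × 56/90 = 6.2. To record 10, the true effect must be 10 × 90/56 = 16.1.
- Shared count s = 36 × 34/90 = 13.6. Control 13.6 + 32 × 56/90 = 33.51; HCEM 13.6 + 29 × 56/90 = 31.64.
- Difference 1.87 days instead of 3; rate ratio 0.944 instead of 29/32 = 0.906. This takes 32 and 29 as fully post-randomisation values.

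**The plan's power figure.** Section 7.4 states power above 90%. With log(32/29) = 0.0984:
- Follow-up contrast only: SE = √[(1/32 + 1/29)/100] = 0.0256, power 97%.
- Interaction averaged over both follow-ups: SE = √{[(1/32 + 1/29)/2 + 2/36]/100} = 0.0297, power 91%.
- Interaction at one follow-up: SE = √[(1/32 + 1/29 + 2/36)/100] = 0.0348, power 81%.

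The stated figure is reproduced by the first two contrasts but not by the third. That shortfall exists before any dilution.

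**Single week-8 interaction, day 56.**
- 90-day window: effect log(33.51/31.64) = 0.0573. Model-based SE = √[(2/36 + 1/33.51 + 1/31.64)/100] = 0.0342, power 39%.
- The same, allowing for the shared days (variance per arm 1/m + 1/36 - 2s/(36m), where m is that arm's week-8 mean): SE 0.0266, power 58%.
- Only the 56 post-randomisation days, with an offset (means 19.9 and 18.0): effect 0.0984, SE 0.0401, power 69%.

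**Averaged interaction, day 56.** 91% undiluted; 75% (model-based) or 87% (shared days allowed for) with the 90-day window; 88% restricted.

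**Between-woman variation in response.** A simulated change-score test at day 56 included the shared days and assumed an intercept SD of 0.5 on the log scale. Power, 90-day against restricted:
- response SD 0: 51% against 60%
- 0.2: 39% against 44%
- 0.3: 29% against 31%
- 0.4: 25% against 25%

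Repeat runs agreed to within a few points, with a gain of 9-10 points at SD 0 and 1-2 at SD 0.4. The documents give no variance, so every SD here, including zero, is an assumption.

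**Validity.** In null simulations with the shared days in both counts, type I error was about 1.3-1.5% with a model-based test and 5-6% with a subject-clustered variance.

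**The case against.** The strongest reply is that the premise is conditional. The sentence in 5.5.2 can tie 90 days to baseline alone, and 7.0 is a general sentence that does not name week 8. If a shorter week-8 window was meant, there is no dilution. A window common to both arms is then absorbed by the time effect of the log-link model, and an offset is needed only if window length varies between women. This stands as a limit on certainty, but the primary outcome then lacks a stated window, which also needs correcting.

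Second, actual visits may not fall on day 56, given Table 1's 19-28 week slot. This stands too. Overlap would be smaller at later visits and would differ between women.

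Third, a common recall length at every visit is a defensible choice, and changing a primary outcome during a trial is not free. The 90-day count can indeed be kept, but as a supporting analysis.

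Fourth, a reader might infer that the window alone cuts power from above 90% to 39%. The documents do not support that. The 39% belongs to a contrast that reaches only 81% before dilution, it takes model-based errors that 7.0 does not specify, and it assumes no variation in response. Section 7.4 also applies 32 against 29 to any follow-up; if those figures already describe the week-8 measure as collected, there is no further power loss.

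**Conclusion.** The point holds as a correctable weakness in how the primary outcome is defined. The text leaves two readings open, and 7.0 favours 90 days. On that reading, at day 56, 38% of the window cannot respond to treatment and an absolute effect is recorded at 62% of its size. This rests on a constant rate within each period and an effect that starts at randomisation.

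A reader might go further and infer that the comparison is biased toward finding an effect. It is not: pre-randomisation days have equal expectation in the two arms, and the null simulations show no material inflation of type I error. The error is toward no difference. The loss of power is real in direction but uncertain in size. For the single week-8 interaction, restriction gains 11 to 30 points (69% against 58% or 39%) under pure Poisson variance, and a few points or less once response varies appreciably between women. For the averaged interaction the gain is about 1 point if the shared days are already allowed for.

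**What to change.** In 5.5.2, 5.5.3 and 7.0:
- State the week-8 window. If a shorter one was already intended, give its length.
- Define the week-8 USO, alcohol and drug outcomes on TLFB days since randomisation. Use log(days assessed) as offset in the count models, with baseline kept as a 90-day rate. Percent days abstinent needs only the restriction.
- Base the week-8 binary inference on the between-arm comparison.
- Keep the 90-day count as a sensitivity analysis.

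In 7.4, restate power for the week-8 contrast that will be tested, with its variance assumptions.

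Make the change by dated amendment before anyone sees unblinded outcome data. No new data are needed: the TLFB is calendar-assisted and, in the plan's words, "provides a way to cue memory so that accurate recall is enhanced for event-level data". The cost is wording in the three sections, the amendment, and a rerun of the power simulation. The statistical downside is fewer events per woman (about 20 against 18 days instead of 34 against 32) and a 56-day binary outcome that cannot be compared directly with the 90-day baseline.
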